Psychological well-being and person-specific levels of social interaction (i.e., changes in social engagement measured with the I-CONNECT Weekly Questionnaire administered weekly via telephone) will be monitored and controlled in the analyses along with other relevant variables, including APOE 4 status.

Video chats will be recorded and analyzed to determine longitudinal changes in speech patterns.

A. Analyses for Primary Outcomes

MoCA test scores (global cognitive function) are our primary outcome.

Secondary outcomes include: neuropsychological test results in the area of language-based executive function, measured by the T-Cog category fluency test (animals), and memory domains measured by

two T-Cog episodic memory tests (Craft Story Immediate and Delayed Recall). We will allocate a type I error rate of 0.05 for our primary outcome. The results will be cross-validated with NIH Toolbox cognitive batteries as exploratory analyses for those who had NIH Toolbox cognitive assessments. Potential mediation variables include the Psychological Well-Being portion of the NIH Toolbox. If Psychological Well-Being shows significant improvement in the experimental group compared to the control group over 6 months (in univariate analysis using $p < 0.05$), the measurement(s) will be examined as potential mediation factors in statistical models as secondary analyses. The Psychological Well-Being portion of the NIH Toolbox consists of 3 measurements: Positive Affect, Life Satisfaction, and Meaning and Purpose. The questionnaire and references for these scales are detailed in: <http://www.nihtoolbox.org/WhatAndWhy/Emotion/PsychologicalWell-Being/Pages/default.aspx>.

B. Sample Size Estimate

Our previous pilot study (based on a six-week intervention) showed Cohen's $d=0.53$ when comparing pre-post changes in language-based executive functions (Clinical Dementia Rating 0 and 0.5 groups combined) in the control and experimental arms. The sample size ($n=72$ completers for each group) in this trial provides 80% power to detect this difference at $\alpha=0.025$, using a two-tailed test (i.e., total type I error rate= 0.025), based on simulation results using non-pooled standard deviation (SD).

Two separate hypotheses are proposed. Stage I examines the efficacy of the high dose and Stage II examines the efficacy of the maintenance dose. Participants covered under the current protocol will be included into the high dose analysis

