The analysis of the New Aim 4 investigated the effectiveness of language markers from conversation in detecting early MCI subjects, where the key hypotheses are that 1) data-driven language and acoustic markers are predictive of early MCI subjects, 2) behavior markers from CART study are predictive of early MCI subjects, and 3) fuse both data to further improve the ability of identifying MCI

Aim 4 (1): To validate the first hypothesis of effectiveness of language and acoustic markers, we will first pre-process the data and extract acoustic markers and linguistic markers. We will apply automatic speech recognition (ASR) models to convert the collected conversations to machine-readable text in computer. We will then use OpenSMILE to extract Mel-frequency cepstral coefficients (MFCC) from the raw acoustic recordings as acoustic features in our analysis. For each recording, we will compute various types of feature representations (hand-crafted, statistical, and deep) from the MFCC features and compare them using their quality as evaluated in downstream analysis. Next, we will investigate one conventional bag-of-words feature representation using linguistic Inquiry and Word Count (LIWC) and deep-learning based embeddings.

We will first investigate the correlation of the two linguistic feature representations and their effect on classification performance on MCI detection. We will then compare the inclusion of MFCC features and investigate the effects on the classification performance. For classification models, we will use the de-identified interview data from I-CONNECT to assess the performance of the multi-modal predictive models using standard performance measures such as the area under the ROC curve (AUC), sensitivity, specificity, etc. We will randomly divide the data into three sets (80% for training, 10% for validation, and 10% for test), and perform 10-fold cross-validation to minimize the variability in the training set. Stochastic gradient descent will be used for training deep learning models, and first-order gradient descent will be used for non-deep learners. To compare the performance of different algorithms, we will compute the p-value to measure the significance of improvements over the 10-fold evaluations.

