Aim 4 (2): To validate the hypothesis of the effectiveness of behavior markers, we will first perform missing value evaluation to estimate the missing values in the sensor-based monitoring data CART. We will use the missing rate as a metric of the uncertainty of the estimation and take the factor into account when making predictions. For modeling with long-term sequences, we will investigate the effectiveness of various imputation strategies, including commonly used smoothing-based imputation techniques (e.g., carrying next forward, carrying last backward, multiple imputation with chained equations, etc.), as well as model-based imputation using matrix completion and deep learning-based imputation methods. After we are done with the imputation, we will then develop a two-level multi-granularity feature extraction process with fine-granularity features describing short-term behavior patterns, and coarse-granularity features describing long-term ones. We will use a denoising autoencoder (DAE) model to extract a low-dimensional latent feature vector, a recurrent neural network to learn the temporal patterns over the fine-granularity features extracted from DAEs. We will then build classification models from the multi-granularity features extracted and study its effectiveness, using the same training-testing scheme (training and testing procedures, evaluation metrics) mentioned above.

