Aim 4 (3): By fusing both data using information collected in both data (NACC UDS V3), we will examine whether combining linguistic/acoustic features (coming from I-CONNECT) and behavioral markers (coming from CART) can further improve the identification of MCI. We will conduct a joint analysis of language and behavior markers using a novel information fusion framework. In this analysis, we will conduct patient similarity evaluation using NACC UDS data, by using a generalized Mahalanobis distance derived from UDS data. Once the patient similarities are measured, we will use behavior feature vectors from similar patients to construct auxiliary variables. Once done, we will investigate two ways of constructing the enriched feature representations: 1) simple concatenation: the original patient vector representation and the vector representations for similar patients will be simply concatenated to form a long vector which will be feed into the MCI classifiers. 2) hierarchical concatenation: the representations of the similar patients will be aggregated first, and then the aggregated vector will be concatenated with the original patient representation vector. For the classification model, we plan to investigate both conventional models such as logistic regression and decision tree, as well as advanced models such as gradient boosted decision tree and multi-layer perceptron. We will use the same evaluation metrics as done in last hypothesis.

IX. Privacy, Confidentiality and Data Security

Privacy, confidentiality, and data security approaches for this Remote Protocol remain the same as those utilized in the main I-CONNECT study protocol.

X. Risks and Benefits

A. Potential Risks to Subjects

1. Privacy

There is a risk of loss of confidentiality. All study personnel will receive training about HIPAA and the responsibilities that accompany the conduct of research. Subject confidentiality will be protected in compliance with OHSU, research site, and HIPAA guidelines.

2. Emotional Risk

Subjects receiving the intervention may feel lonely and isolated at the end of the trial when the intervention has concluded. They may form emotional attachments to the conversation staff and feel a sense of loss or sadness.

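### Aim 4 compares algorithms with a p-value over ten cross-validation folds and makes no allowance for overlapping training sets; a plain paired t-test would have roughly two to three times its nominal error rate

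*Combined protocol and SAP*

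**What the plan says.** The scheme is set out in section VIII.C of the combined protocol and SAP, under Aim 4 (1). The data are split at random ("80% for training, 10% for validation, and 10% for test"), and the analysts will "perform 10-fold cross-validation to minimize the variability in the training set". Performance is described by AUC, sensitivity, specificity and similar measures. The rule for choosing between algorithms is: "we will compute the p-value to measure the significance of improvements over the 10-fold evaluations".

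Nothing further is said about that p-value. The test, the metric it is applied to, its sidedness, its alpha and any correction for dependence between folds are all left open. Acoustic features are computed for each recording, and the section does not say whether one participant's recordings stay in the same fold.

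The two later parts refer back in different terms. Aim 4 (2) builds and studies its models "using the same training-testing scheme (training and testing procedures, evaluation metrics) mentioned above". Aim 4 (3) says only: "We will use the same evaluation metrics as done in last hypothesis".

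Section II labels Aim 4 exploratory. The only error-rate allocation in section VIII.A concerns a different endpoint: "We will allocate a type I error rate of 0.05 for our primary outcome".

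**The concern.** The sentence makes the ten fold evaluations the unit of inference. Those evaluations are not ten independent observations, because the models behind them are trained largely on the same people. Differences in performance between two algorithms therefore tend to move together across folds. A test that takes the spread of the ten differences and divides by ten, as for independent data, gives too small a standard error.

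At stake are the claims that one algorithm improves on another. The clearest case is in Aim 4 (1), where adding acoustic (MFCC) features to linguistic ones is to be assessed. The hypothesis that fusing the two data sources improves identification of MCI is of the same kind. If the p-value is too small in each such comparison, some improvements will be reported as significant when there is none.

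**Working it through.** The plan states no error rate for this comparison, so there is no figure of its own to reproduce.

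**Inputs from section VIII.C.** Ten folds. The test-to-training ratio is 10/80 = 1/8 as written, or 10/90 = 1/9 if plain 10-fold is run without a separate validation set.

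**Assumed, because the documents do not give them.** A paired t-test on the ten fold differences (9 df), two-sided at 5%, and a between-fold correlation rho.

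**1. Overlap of training sets.** In plain 10-fold, two training sets of nine folds share eight: 80/90 = 89%. With an 80/10/10 rotation, two training sets together leave out at most four folds, so they share at least 60/80 = 75%.

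**2. Variance ratio.** For ten equally correlated differences, true variance / naive variance = (1 + 9·rho)/(1 − rho). The usual heuristic sets rho to the test fraction, which gives the corrected resampled form (1/10 + n_test/n_train)/(1/10).

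- Ratio 1/9 (rho = 0.10): (0.1 + 0.1111)/0.1 = 2.111; square root 1.453.
- Ratio 1/8 (rho = 1/9): (0.1 + 0.125)/0.1 = 2.25; square root 1.500.

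**3. True size of the nominal 5% test.** The critical value on 9 df is 2.262.

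- P(|t9| > 2.262/1.453) = 15.4%.
- P(|t9| > 2.262/1.500) = 16.6%.

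**4. Sensitivity to the assumed rho**, same test:

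| rho | true error rate |
|---|---|
| 0 | 5.0% |
| 0.02 | 6.9% |
| 0.05 | 10.0% |
| 0.10 | 15.4% |
| 1/9 | 16.6% |
| 0.20 | 25.7% |
| 0.30 | 35.1% |

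**5. Sensitivity to the assumed test**, at rho 0.10 to 1/9: a one-sided 5% t-test gives 11.9% to 12.6%, and a two-sided z-test gives 17.7% to 19.1%.

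**6. Simulation without the heuristic.** Two equally good linear classifiers on independent feature sets were compared by 10-fold cross-validation with an 80/10/10 split and one record per participant. Assumed settings were 80, 144 or 186 participants and 10 or 40 features, with 1,500 replicates each. The naive t-test rejected in 9.9% to 14.7% of replicates with AUC and in 9.1% to 11.7% with accuracy (implied rho about 0.04 to 0.09). At a rate of 10% the simulation error is sqrt(0.10 × 0.90/1500) = 0.8 percentage points, so every setting is clearly above 5%. Adding features to an existing set was not simulated.

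**7. Repeated recordings.** With 80 participants, ten recordings each (assumed), AUC and 600 replicates, the rate was 13.2% when folds were split by participant and 31.3% when split by recording.

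**The case against.** The strongest reply is that the plan leaves the test unspecified and does not commit to a wrong one. Nowhere does it say that the folds are treated as independent, and a corrected resampled t-test would fit the same sentence. That is true, and it makes the size conditional. It does not remove the point: the plain reading of a p-value over ten evaluations is the uncorrected test, and nothing in section VIII.C rules it out.

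The second reply concerns the number. A reader might infer that the comparison simply has a true error rate of 15% to 17%. The documents do not support that. They give no alpha for Aim 4, no test and no correlation, and the participant-level simulations fall below that band. The direction is firm for any positive correlation; the single figure is not.

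The third concerns scope. A reader might infer that all of Aim 4's hypotheses are decided by this p-value. They are not. The first two hypotheses say that the markers are predictive, and performance is described by AUC, sensitivity and specificity. The p-value is confined to comparing algorithms. The fusion hypothesis is comparative, but Aim 4 (3) carries over only the evaluation metrics, so use of the p-value there is an inference. Aim 4 (2) adopts the training and testing scheme, yet does not itself announce a test between models.

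The last reply is that Aim 4 is exploratory. This limits the consequence and would excuse the absence of multiplicity control. It does not make a p-value valid for the single comparison it is attached to.

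**Conclusion.** The concern holds in conditional form. If the comparison is run as a two-sided 5% paired t-test on ten fold scores, its true error rate is about 15% to 17% under the test-fraction correlation and about 9% to 15% in simple simulations with one record per participant. That is roughly two to three times nominal. It may be higher if recordings from one participant fall in different folds; the 31.3% above illustrates this and is not an estimate for this trial.

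The algorithm comparisons in Aim 4 (1) are affected directly. Those in Aim 4 (2) are affected if the same scheme is used to compare models, and the fusion comparison in Aim 4 (3) if the same p-value is applied there. Overlap between training sets does not by itself undermine the AUC, sensitivity and specificity estimates. The MoCA primary outcome and the randomized comparison are not touched. The change is worth making because a better method is readily available, but the exploratory status of the aim keeps the point below the level of the main analysis.

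**What to change.** In section VIII.C:

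- Assign folds by participant, so that all recordings from one person fall in the same fold.
- Replace the fold-level p-value with a paired comparison on pooled out-of-fold predictions, using a participant-level bootstrap or a paired AUC test with one score per participant. This treats the fitted models as given, which should be stated.
- Alternatively, use the corrected resampled t-test with the n_test/n_train term. In the two-sided 5% case, the cut-off on the naive |t| rises from 2.262 to 2.262 × 1.453 = 3.29 (ratio 1/9) or 2.262 × 1.500 = 3.39 (ratio 1/8). This is approximate, because it restores 5% only if the assumed correlation is right.
- Name the metric, alpha and sidedness.
- State that the same rule applies to every algorithm comparison in Aims 4 (1) to 4 (3).

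The cost is a few lines of code and no new data. Intervals will be wider, and fewer improvements will be declared significant.

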3. Fuse CART digital biomarker data and I-CONNECT language markers to further boost the model screening performance.

III. Background

In recognition of the COVID-19 public health threat, Oregon Health & Science University suspended all in-person, *nonessential research on human subjects* on March 15th, 2020. The governor of Oregon went on to issue a stay-at-home order shortly thereafter. These restrictions lifted enough to permit remote trial

conduct and contactless materials delivery to subjects by June 8th. However, given the ongoing pandemic and uncertainty around possibly future COVID-19 restrictions, as well as the high-risk nature of our subject population (adults age 75 and older), it became necessary to adapt the protocol for remote conduct.

IV. Study Design

This study is a two-arm randomized controlled trial.

Participants will be randomized in a 1:1 ratio to the experimental or control conditions balancing the following factors:

- Cognitive status (healthy normal vs. MCI)
- Age (age 75-79 vs. age 80-84 vs. over 85+)
- Education (high school completion vs. below high school education)
- Sex (male vs. female)
- Mean Montreal Cognitive Assessment (MoCA)

Subjects will complete in-home assessments at the 6-month time point. All subjects will receive a follow-up telephone call approximately one month after the intervention period concludes. Subject participation in the study will last approximately seven months including the screening and follow-up period. In total, there are approximately four scheduled assessment calls (if assessment time points are split into multiple calls), plus additional technology troubleshooting calls, depending on group allocation.

A. Intervention Group

Half of participants will be randomized to the experimental group, the study intervention group. These subjects will engage in video chat conversations with study staff using an online video communication platform. Each video chat session will be 30 minutes long. Subjects will also receive a weekly telephone call, lasting approximately 10-15 minutes, to assess health and social activities.

The intervention period will last 24 weeks. Subjects in the intervention group will receive four chats per week (a high dose of the video chat intervention) for 24 weeks. The video chat frequency will then taper to a decreased dose of two chats per week during weeks 25 and 26 of the follow-up period.

B. Control Group

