Subjects may choose to provide contact information for a contact person the study team may call in the event the study team cannot successfully reach the participant. Subjects may choose to provide contact information for their primary care physician, if they would like their physician to be notified in the event that clinically relevant information is noted in the course of the study (e.g. the subject is assessed as developing dementia).

3. Resource Provision *Month 6, Failed Screening, Early Termination/Withdrawal*

At the Month 6 time point, study staff will provide participants with post-study resources for social engagement, and will encourage participants to utilize the resources. Subjects will also receive this information if they fail screening, or if their participation is terminated early or they withdraw from the study. If participants become depressed, as evidenced by their scores on the Geriatric Depression Scale (GDS), staff will provide information about mental health resources and may refer the subject to the subject's primary care physician. Subjects should be encouraged to utilize the provided resources again at the final follow-up call.

C. Cognitive & Functional Assessments

1. Neuropsychological Battery *Screening, Month 6*

Subjects will receive the Uniform Data Set (UDS) Version 3 Telephone Administered Cognitive Battery, or T-Cog, after the COVID-19 pandemic started. This battery is the telephone version of the National Alzheimer's Coordinating Center (NACC) UDS Version 3, used by the Alzheimer's Disease Centers (ADC) program of the National Institute on Aging (NIA).

The battery consists of brief measures of attention, processing speed, executive function, episodic memory, and language. Tests include: Craft Story Immediate Recall, Blind/Telephone MoCA, Number Span Forward, Number Span Backward, Category Fluency (Animals), Category Fluency (Vegetables), Oral Trail Making Test Part A, Oral Trail Making Test Part B, Craft Story Delayed Recall, Verbal Fluency (F), and Verbal Fluency (L).

Administration of the battery will be audio recorded. Due to the need to ensure appropriate delay timing for memory assessments, the neuropsychological battery assessments must be completed in the order presented above.

The battery data measured at the Screening time point will be used as the subject's baseline for data analysis.

2. Clinical Dementia Rating (CDR) (NACC Form B4, Adapted) Screening, Month 6

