The CDR assesses dementia symptoms in a variety of domains and provides an overall rating of dementia symptom severity. Due to the socially isolated nature of the population, the CDR assessment will be limited to the subject. No informant will be used. It will be used in conjunction with the neuropsychological battery to identify participants as having normal cognition, MCI, or dementia, and to determine participant eligibility.

3. The NIH Toolbox Emotional Domain Baseline, Month 6

The NIH Toolbox is a proctored (i.e., requires active administrator participation) assessment program administered via electronic tablet. To adapt this assessment to be conducted remotely, subjects will complete only the emotional domain of the Toolbox as questionnaires.

The toolbox measure of emotion includes four general domains: negative affect (anger, fear, and sadness), psychological well-being (positive affect, general life satisfaction, and meaning & purpose), stress & self-efficacy (perceived stress and self-efficacy), and social relationships (social support, companionship, and social distress).

D. Subject Health Assessments

1. Subject Health History (NACC Form A5, Adapted) Screening

Subject medical history will be collected, including substance use history.

2. Medication Assessment Screening, Month 6

A list of the subject's current medications and general information about medication habits will be collected.

3. Geriatric Depression Scale (GDS) (NACC Form B6) Screening, Month 6, Follow-Up

The GDS is a self-report assessment of depression. If the subject scores ≥ 2 on the suicide ideation subscale of the GDS, the subject will be assessed for possible suicidal ideation using a depression safety tool, and staff will take appropriate follow-up actions per the tool's guidance.

The GDS will be used to assess subject eligibility at screening. If subjects are excluded due to high GDS score, depression resources will be provided and the subject may be referred to their primary care provider.

4. Family History of Dementia *Baseline*

Subject family history of dementia will be collected.

5. Physical Evaluation Form (NACC Form B1) *Baseline*

The subject will self-report on height, weight, vision and hearing.

E. Eligibility *Following clinician diagnosis*

A telephone pre-screening will be conducted to assess preliminary subject eligibility. If successful, a full Screening visit will be conducted to further assess eligibility.

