If the subject is determined to be ineligible during Screening, the visit will be ended at that point. Otherwise, final study eligibility will be determined upon clinician diagnosis of subject cognitive status following the screening assessments. If a subject is found ineligible, staff will provide the subject with a list of resources for social engagement.

Previously ineligible subjects may be rescreened for participation in the study if their eligibility status is believed to have changed. Their subject identification code will be kept the same; a new code will not be assigned. If fewer than 6 months have elapsed since the original administration of the Screening cognitive assessments, the neuropsychological battery will not be repeated due to possible learning effects. The original scores will be used. Subjects will not receive additional compensation for rescreening. Other Screening procedures will be repeated per the Schedule of Events, including collection of informed consent.

F. Clinician Diagnosis (NACC Form D1) *Within 1 week of Screening, Month 6*

Once all Screening procedures have been completed, subject CDR and neuropsychological test results should be evaluated by the study site's designated neuropsychologist within approximately one week. The clinician will complete a clinician diagnosis, which identifies participants as having normal cognition, MCI, or dementia. Subjects must have normal cognition or MCI to be eligible to participate in the study. Subject MCI will be further characterized as amnesic or non-amnesic. If the site neuropsychologist is uncertain about the diagnosis, (s)he may consult with the designated trial neuropsychologist at other study site(s). The clinician diagnosis will be reconfirmed within approximately one week after the Month 6 assessments to monitor the subject's cognitive status, as this study will not include subjects with dementia.

G. Randomization *Following eligibility determination*

Subjects with normal cognition or MCI per clinician diagnosis will be randomized to the intervention group or to the control group once the clinician diagnosis is available to confirm subject eligibility. This should be completed as soon as possible once the required eligibility confirmation is available.

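### Aim 4 (3) picks CART donors by UDS data that also feed the MCI label, so a fusion gain over language alone does not by itself show that behaviour markers add to language

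*Combined protocol and SAP*

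**What the plan says.** Section II, Aim 4 item 3, gives the purpose: "Fuse CART digital biomarker data and I-CONNECT language markers to further boost the model screening performance". Section VIII.C, Aim 4 (3), gives the method. Similarity comes first: "we will conduct patient similarity evaluation using NACC UDS data, by using a generalized Mahalanobis distance derived from UDS data". Then "we will use behavior feature vectors from similar patients to construct auxiliary variables", and these are joined to the participant's own vector, either one by one or after aggregation, and passed to an MCI classifier. UDS V3 is the only link named between the two data sets. On evaluation the text says only "We will use the same evaluation metrics as done in last hypothesis". No reference model is named. That the reference is language alone is implied by the aim of improving identification further.

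The label is described elsewhere. Section VI.C.1: "Subjects will receive the Uniform Data Set (UDS) Version 3 Telephone Administered Cognitive Battery, or T-Cog". Section VI.C.2 says of the CDR: "It will be used in conjunction with the neuropsychological battery to identify participants as having normal cognition, MCI, or dementia". Section VI.F says that "subject CDR and neuropsychological test results should be evaluated by the study" site's neuropsychologist, who then assigns normal cognition, MCI or dementia.

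**The concern.** The third key hypothesis in Section VIII.C is that fusing the two data sources improves identification of MCI. If the fused model beats language alone, the natural reading is that in-home behaviour carries information that speech does not. The planned comparison cannot separate that from a second explanation: the donor vectors encode where the recipient stands on the tests from which the diagnosis was made.

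There is also a practical side. The stated goal is screening, and the fused model cannot be run without UDS data on the person being screened. The comparator with the same inputs is therefore language + UDS, and the plan does not include it.

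**Working it through.** The documents give no sample size, effect size or expected AUC for Aim 4, so there is no planned figure to reproduce. The check has a structural part and an illustrative simulation.

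**Structure.** Let U be a recipient's UDS data, L the language features, Y the MCI label, and B_j the behaviour vector of CART participant j. With k nearest donors averaged,

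A = (1/k) × sum of B_j over the k participants with the smallest distance D(U, U_j).

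For a given CART pool and distance, A is fixed once U is known. Two things follow.

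1. If U informs Y, A can inform Y even when B is unrelated to cognition.
2. Once U and L are in the model, A carries no further information on Y. It can help only by offering a different functional form of U.

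This takes the donors to be CART participants who are not themselves recipients. That is the natural reading of Aim 4 (3), but the text does not say so outright.

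**Simulation inputs, all assumed.** There are 72 recipients: only the intervention arm has chats, and Section VIII.B plans 72 completers per arm. Half have MCI, and there are 200 donors. Eight UDS scores load 0.6 on one factor. The label is the standardised UDS composite plus noise of SD 0.6 or 1.0, split at the median. There are five language and five behaviour features. Classification is ridge logistic with stratified 10-fold cross-validation by participant. Donors are averaged unless stated. Ranges cover both noise levels.

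| Behaviour in CART | Language AUC | Language + donors |
|---|---|---|
| Tracks UDS, r = 0.2-0.4, k = 10 | about 0.63 | 0.70-0.81 |
| Tracks UDS, r = 0.2-0.4, k = 20 | about 0.63 | 0.72-0.85 |
| Tracks UDS, r = 0.2-0.4, k = 10 or 20 | 0.76 | 0.79-0.88 |
| Pure noise | about 0.63 | gain up to about 0.05 |
| Pure noise | 0.76 | about no gain |
| Matching on non-diagnostic items only | 0.63 | 0.60 |

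In the tracking rows the apparent gain at language AUC 0.63 is 0.70 − 0.63 = 0.07 to 0.81 − 0.63 = 0.18 with 10 donors, and 0.09 to 0.22 with 20. At 0.76 it is 0.03 to 0.12. Language + UDS has AUC 0.80-0.91 in the tracking runs, and adding donor vectors changes it by about −0.005 to −0.015.

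Simple concatenation of 10 donors gives less. At language AUC 0.76 it gains only at r = 0.4 with the lower label noise (0.76 to 0.80).

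**Second set of settings** (90 or 186 recipients, 100 donors, five UDS scores, 10 or 50 behaviour features, 1, 5 or 10 donors). With pure-noise behaviour, UDS-matched donors changed AUC over language alone by −0.025 to +0.175, upward in 10 of 12 cells. The same noise from randomly chosen donors lowered AUC in all 12. In none of 36 cells did donor vectors improve on language + UDS (change −0.007 to −0.055).

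**Power of the like-for-like comparison.** CART behaviour was then made to predict the label beyond UDS (five markers, d = 0.3-0.8). Language + UDS + donors beat language + UDS in 0-0.2% of runs (corrected resampled t, one-sided 2.5%). This is consequence 2 above: the comparison cannot detect a behaviour effect that is really there.

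**A test that can detect it.** Within CART, compare UDS + own behaviour with UDS. It never passed when behaviour only tracked UDS. At d = 0.5 its power was 11-30% with 200 participants and 48-79% with 400.

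**The case against.** - *The UDS items may be harmless.* The NACC forms in the schedule include demographics, health history and physical evaluation, and matching on non-diagnostic items gave no gain. This stands as a limit on size. But Aim 4 (3) sets no such restriction.
- *Behaviour already has a direct test.* Aim 4 (2) builds MCI classifiers from CART participants' own features, so the behaviour hypothesis does not rest on fusion. This stands. That test does not address whether behaviour adds to UDS or to language.
- *The goal is performance, not attribution.* Partly so. A gain is still a gain, but it should be judged against a model with the same inputs, and Aim 4 (3) does ask what combining language with behaviour achieves.
- *Requiring a gain over language + UDS before behaviour is credited would amount to a ban.* This stands, given the near-zero power. That comparison should be reported and not used as a gate.

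Three stronger inferences are tempting and unsupported. A reader might infer that the fusion analysis is circular and any gain an artefact, or even that the diagnosis form enters the distance; the items are not stated, so neither can be asserted. A reader might infer that behaviour markers do not help if donor vectors fail to improve language + UDS; that result is expected either way. And a reader might infer damage to the trial's results; Section II labels Aim 4 exploratory secondary analysis, and the MoCA analysis does not use it.

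**Conclusion.** The point holds in a limited form. As written, a fusion gain over language alone is not by itself evidence that behaviour markers add to language, because the donor vectors are a function of UDS data that may include the tests behind the label. The language-alone reference is itself only implied.

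The size cannot be taken from the documents. Under the assumptions shown it runs from nothing (non-diagnostic matching items, or noise behaviour with language AUC 0.76) to about 0.2 in AUC (behaviour tracking UDS, weak language signal, 20 donors). The noise-only gain is small with five behaviour features but was larger in some cells of the second set of settings. These figures show the mechanism and do not forecast the result. How CART assigns MCI status is not described here.

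Severity is low: this is one part of an exploratory aim, and no trial outcome is affected. Missing detail in Aim 4 (1) on the fold test and the unit of splitting is a separate matter and forms no part of this point.

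**What to change.** Keep the fusion method and add to Section VIII.C, Aim 4 (3):

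> The UDS items entering the distance are listed before analysis. Four models are reported with the same UDS items, classifiers and folds: language; language + donor vectors; language + UDS; language + UDS + donor vectors. A gain of the second over the first is described as a gain from UDS-matched enrichment and not as evidence that behaviour adds to language. Failure of the fourth to exceed the third is not evidence against behaviour markers.

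Add to Aim 4 (2):

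> Within CART, UDS + own behaviour is compared with UDS alone, as the evidence on behaviour beyond UDS. The power of this comparison at the available sample size is stated.

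The cost is a little more analysis on data that Aim 4 already uses, and a narrower claim from the fusion result. The CART comparison may well be inconclusive: with 200 participants its power at d = 0.5 was at most 30% under the assumptions above.
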